3. Award determination by VBA: Award determination will also be the dependent measure in proposed secondary analyses. The data collected will be whether any benefit was awarded, and the percentage service connection awarded.

4. The VA databases will be used to identify all non-exclusive psychiatric diagnoses, as defined in the DSM-IV and DSM-V, ICD 9 and ICD 10.

5. Distance from VA: Veterans' addresses collected upon enrollment will be converted into distance from the nearest VA facility using Global Information System (G.I.S.) mapping (Fortney 2000). Participants and VA treatment facilities will be geocoded by street level (the G.I.S. will use the street address) to calculate driving distance as a measure of treatment accessibility. Distance from treatment has been associated with receipt of fewer services (Rost, Fortney et al. 2002).

6. Chart review to determine presence of a substance abuse disorder at time of Compensation.

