3. Approach to Missing Data: We will first determine whether data are missing completely at random using Little’s (1988) test. If data are not missing at random, we will characterize study drop-outs in terms of differences in mean scores on relevant variables. Variables determined to be related to missingness or to the incomplete variables (missing data correlates) will be included in models to improve estimation.

For analyses involving hierarchical linear modeling, maximum likelihood estimation techniques permit missing data on the dependent variable. Valid parameters are estimated from all available data from all cases under the assumption that data are missing at random. To improve the plausibility of the missing-at-random assumption, we may include missing data correlates in the model.

For normal models (ANOVA, Regression), if data are not missing-at-random, we will use NORM software to multiply impute missing values. We will combine parameter estimates and estimate standard errors according to Rubin’s rules (cited in Schafer, 1997).

4. Analysis of the Effect of Substance Use on PTSD, Treatment Attendance (Evaluative Specific Aim 1-- Veterans with substance use disorders randomized to No-Additional-Treatment will have worse PTSD over time compared to Veterans without substance use disorders and will attend fewer weeks of mental health and/or substance abuse treatment):

The principal strategy for assessing the effect of substance use on outcomes (CAPS score, weeks attending any mental health and/or substance abuse treatment) will be random effects regression, also called HLM or hierarchical linear modeling. An individual’s behavior on the outcome variable is modeled as a function of an individual growth trajectory (and thus does not require all participants to have data at all measurement points), and then, at a between participants level, the parameters of the individual trajectories are analyzed by group. The focus of these analyses will be the ‘substance use status by time effects’ for each hypothesis. These effects will evaluate whether the slopes, or rates of change, of one group differ from the slopes of another group. The effects of (site) and (site X substance use) status will be modeled.

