Because substance use is not randomly assigned, potentially confounding baseline covariates will be considered in the analyses. Baseline level of the dependent variable, e.g. CAPS-rated PTSD severity, will be included in the analysis as a covariate. Other covariates will be included that have been associated with substance use that also might potentially be associated with the outcomes being studied, i.e. PTSD severity and treatment attendance. The covariates will include gender, education level (years of study), current employment status, depression severity (as assessed by the BDI), response to stressful experiences, and meeting criteria for TBI (as assessed by the baseline questionnaire).

We will also examine the within-subjects relationship between the substance use and PTSD outcomes. We hypothesize that improvements in substance use will correspond with improvements in PTSD as evidenced by a significant positive correlation between the slopes of substance use measures (e.g. abstinence, heavy drinking days) and CAPS scores. We also plan to utilize a Structural Equation Model that has the combined benefits of latent curve, autoregressive, and time-specific lagged effects analyses (Bollen & Curran, 2004). We will

analyze the immediate and lagged effects of substance use on CAPS scores. The same approach will be applied to elucidate the relationship between substance use and treatment attendance. Additionally, we will analyze the nature of the effect of each outcome at the previous time point (time t-1) on the value of the same outcome at the current time point (time t). In this manner, we will determine the unique and combined effects of all influences on PTSD symptoms and treatment attendance.

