#### 5. Analyses of the Relationship Between Attitudes About Compensation examinations and Outcome

*(Evaluative Specific Aim 2: Attendance at treatment will be predicted by Veterans' perceptions that obtaining and maintaining VA benefits depends on attending PTSD treatment):*

We hypothesize and will test in HLM regression models whether attendance at substance abuse and/or mental health treatment (and other outcomes) are predicted by the following, after accounting for appropriate covariates:

a. Veterans' perception that obtaining and maintaining VA benefits depends on treatment. Veterans' perceptions concerning the linkage between their status and receiving benefits will be derived for the three scales of the Disability Beliefs Scale which reflect perceived linkage of benefits to: (i) engagement in VA mental health treatment, (ii) being symptomatic from PTSD, and (iii) being abstinent from drugs and/or alcohol. Other scales will be analyzed if the factor analysis of the Disability Beliefs scale reveals another factor structure.

b. Subscales indicating that (i) Validation, (ii) Self-Other Considerations and (iii) Financial concerns were Veterans' reasons for seeking Compensation, as rated on the Disability Application Appraisal Inventory (Sayer, Spoont et al. 2004). We hypothesize that Veterans who rate themselves higher in having applied seeking "Validation (of being ill)" will be more likely to attend treatment, and that Veterans with higher ratings in "Self-Other (e.g. someone else urges Veteran to seek award)" or who applied for financial gain would be less likely to attend treatment.

c. Interactions between Disability Application Appraisal and Disability Beliefs Scale subscale variables. Reasons for seeking benefits and beliefs about disability application appraisal may interact to make treatment attendance more or less likely.

Covariates in these analyses will include those reflecting three main domains that have been associated with treatment attendance (Koenen, Goodwin et al. 2003):

- Predisposing factors: demographic variables (age, gender)
- Enabling factors that facilitate access to treatment: study site, distance between home and medical center calculated using G.I.S. mapping
- Need for treatment: Substance Use, PTSD severity (CAPS total score) and depression severity (Beck Depression Inventory).

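### The Hypothesis 1 covariate list leaves out age and driving distance, which the plan's other attendance model includes, so the user versus non-user contrast is open to avoidable confounding

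*Combined protocol and SAP*

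**What the plan says.** Section J, item 4, tests Evaluative Hypothesis 1: whether users assigned to No-Additional-Treatment have worse PTSD and fewer weeks of treatment than non-users. It acknowledges that substance use is not randomly assigned and gives a rule for choosing covariates: "Other covariates will be included that have been associated with substance use that also might potentially be associated with the outcomes being studied". The list follows: "The covariates will include gender, education level (years of study), current employment status, depression severity (as assessed by the BDI), response to stressful experiences", with TBI status completing it. Two further adjustments are stated: "Baseline level of the dependent variable, e.g. CAPS-rated PTSD severity, will be included in the analysis as a covariate", and "The effects of (site) and (site X substance use) status will be modeled". The tested term is a difference in slopes: "The focus of these analyses will be the ‘substance use status by time effects’ for each hypothesis".

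Section J, item 5, also models attendance. Its covariates come from three domains that the plan describes as related to attendance. They include "Predisposing factors: demographic variables (age, gender" and, as enabling factors, "study site, distance between home and medical center calculated using G.I.S. mapping". Section H, item 5, explains why distance is collected: "Distance from treatment has been associated with receipt of fewer services".

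**The concern.** The two models share an outcome, and each contains substance use: as the exposure in J.4 and as a covariate in J.5. They adjust for different things, and the plan does not say why. If the two estimates for substance use disagree, nothing in the plan says which to believe.

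This matters more in J.4, because measured covariates are what stand between that contrast and confounding. If users were younger than non-users, or lived nearer or farther, and that variable also predicted the course of attendance, part of any user versus non-user gap would reflect age or access. The randomized SBIRT comparison is not affected.

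**Working it through.** **1. The two covariate sets side by side.**

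| Variable | J.4 | J.5 |
|---|---|---|
| Age | not named | named |
| Driving distance | not named | named |
| Gender, site, BDI | included | included |
| CAPS severity | named only as an example of an outcome's own baseline | named |
| Baseline level of the outcome | included | not named |
| Education, employment, stress response, TBI | included | not named |

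Age and distance are absent from J.4 and present in J.5. The CAPS row is a further difference for the attendance model, noted but not pursued here.

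**2. The two selection rules.** J.4 asks for a link with substance use and a possible link with the outcome. J.5 asks only for a link with attendance. The documents supply the outcome link for both variables: age through J.5, distance through J.5 and H.5. They say nothing on whether either variable differs between users and non-users.

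**3. Availability.** Distance is to be calculated from addresses taken at enrollment (H.5). Demographics are collected in the baseline questionnaire (G.4), and age is an eligibility criterion (B.2, 18 to 65 years). No new data collection is needed.

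**4. The tested term.** The focus is status by time. In a linear growth model, a covariate entered only as a main effect shifts the level of each trajectory and leaves the group difference in slopes unadjusted for it. Protecting the tested term needs the covariate's interaction with time. J.4 does not say whether its covariates enter that way. Hypothesis 1 is also worded as fewer weeks attended, which is a level contrast, and for that reading the main effects matter.

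**5. The plan's own figure for this contrast.** Section A, item 2, states power above .80 for a standardized slope difference of .25 with 560 participants, 80 of them users. Alpha is not stated there; two-sided .05 is assumed.
- SE = √(1/80 + 1/480) = 0.121 SD. Power = Φ(0.25/0.1208 − 1.96) = 0.54.
- With an equal split of 280/280, SE = √(2/280) = 0.0845 and power = 0.84.

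The stated power is reproduced by the simple formula only for equal groups. The software's slope-variance inputs are not given, and the present point does not rest on this figure; .25 serves below only as a yardstick.

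**6. Illustration on assumed values.** Bias per covariate = (user minus non-user imbalance, in SD) × (partial standardized association of the covariate with the attendance slope). Assume an imbalance of 0 to 0.5 SD and an association of 0 to 0.3. False-positive rate = P(|Z + bias/SE| > 1.96).

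| Imbalance | Association | Bias (SD) | False-positive rate |
|---|---|---|---|
| 0 | any | 0 | 5.0% |
| 0.2 | 0.2 | 0.04 | 6.3% |
| 0.3 | 0.3 | 0.09 | 11.6% |
| 0.5 | 0.3 | 0.15 | 23.7% |

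The assumed range gives 0 to 0.15 SD against the plan's .25. None of these imbalances or associations comes from the documents. The direction is unknown.

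**The case against.** The strongest reply is that J.4 and J.5 answer different questions. J.5 studies beliefs and adjusts for predictors of attendance; J.4 adjusts for confounders, which must also be linked to substance use. A variable can properly belong in one list and not the other. This stands as a reason not to say that the contrast is confounded. It does not explain the omission, because a confounder set is fixed in advance on plausibility and imbalance need not be proven first.

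Existing adjustment also counts. Site is modeled and may carry part of any access difference. The outcome's baseline level, which for attendance means prior attendance, may absorb part of the effect of stable traits such as age and distance. That could shrink a bias, but it does not address an effect of age or distance on change over time.

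Finally, the list may be open, since it says what the covariates will include. If so, covariates could be added after the results are seen, which is a weaker position than naming them now. Age does appear in section J, item 8, but only in separate exploratory analyses and only if bivariate results suggest it.

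A reader might infer that Hypothesis 1 is biased by a definite amount, for example because users are usually younger. The documents do not support that. They report no age or distance difference between the groups, and a general belief about age and substance use is not evidence for this sample of claimants. Setting an assumed effect of age on attendance level against the .25 difference in slopes would also mix two quantities.

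**Conclusion.** The omission is real: J.4 does not name age or driving distance, J.5 adjusts the same attendance outcome for both, and both are available. This leaves the Hypothesis 1 attendance contrast open to avoidable confounding. For CAPS the point extends to age only, because the plan links distance to use of services and not to PTSD severity. The case is weaker for distance than for age, since site already covers part of access.

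No size can be given from the documents. The bias is zero if the groups do not differ on these variables, or if the variables do not predict the course of the outcome after the planned adjustments. The figures in the working are illustrations over a range that includes zero and should not be read as estimates. This is a free improvement to a stated list.

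**What to change.** In J.4, add age and driving distance, each with its interaction with time, to the attendance model. Add age with its time interaction to the CAPS model. State that these terms are fixed before outcome data are examined. If the sponsor prefers to leave either variable out, one sentence should say why J.4 and J.5 differ. The SAP should also say which distance is meant, since H.5 refers to the nearest VA facility and J.5 to the medical center.

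The cost is SAP wording and, with linear terms, four coefficients in the attendance model (2 variables × 2 terms) and two in the CAPS model, out of 560 participants. Visits, assessments and sample size do not change.

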#### 5. Analyses of the Relationship Between Attitudes About Compensation examinations and Outcome

*(Evaluative Specific Aim 2: Attendance at treatment will be predicted by Veterans' perceptions that obtaining and maintaining VA benefits depends on attending PTSD treatment):*

We hypothesize and will test in HLM regression models whether attendance at substance abuse and/or mental health treatment (and other outcomes) are predicted by the following, after accounting for appropriate covariates:

a. Veterans' perception that obtaining and maintaining VA benefits depends on treatment. Veterans' perceptions concerning the linkage between their status and receiving benefits will be derived for the three scales of the Disability Beliefs Scale which reflect perceived linkage of benefits to: (i) engagement in VA mental health treatment, (ii) being symptomatic from PTSD, and (iii) being abstinent from drugs and/or alcohol. Other scales will be analyzed if the factor analysis of the Disability Beliefs scale reveals another factor structure.

b. Subscales indicating that (i) Validation, (ii) Self-Other Considerations and (iii) Financial concerns were Veterans' reasons for seeking Compensation, as rated on the Disability Application Appraisal Inventory (Sayer, Spoont et al. 2004). We hypothesize that Veterans who rate themselves higher in having applied seeking "Validation (of being ill)" will be more likely to attend treatment, and that Veterans with higher ratings in "Self-Other (e.g. someone else urges Veteran to seek award)" or who applied for financial gain would be less likely to attend treatment.

c. Interactions between Disability Application Appraisal and Disability Beliefs Scale subscale variables. Reasons for seeking benefits and beliefs about disability application appraisal may interact to make treatment attendance more or less likely.

Covariates in these analyses will include those reflecting three main domains that have been associated with treatment attendance (Koenen, Goodwin et al. 2003):

- Predisposing factors: demographic variables (age, gender)
- Enabling factors that facilitate access to treatment: study site, distance between home and medical center calculated using G.I.S. mapping
- Need for treatment: Substance Use, PTSD severity (CAPS total score) and depression severity (Beck Depression Inventory).

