#### 4. Feasibility:

a. Feasibility of Identifying People Applying for Service Connection for Compensation Exams: At both VACT and TVHS, the Compensation and Pension Clinic schedules Veterans who apply for Compensation for examinations, making this clinic an efficient place to identify potential study participants. We have established procedures to recruit Veterans presenting for Compensation examinations in our previous studies.

b. Feasibility of Enrolling 480 Veterans in the Evaluative Component:

Tennessee: During 2009, TVHS was the site for 299 initial PTSD Compensation examinations for OEF/OIF Veterans, including 22 women.

VA Connecticut: After obtaining IRB approval, our group reviewed the VA charts and Compensation examination reports of 62 consecutive OEF/OIF Veterans who underwent Compensation examinations at VA Connecticut for the six-month period between 7/1/08 and 12/31/08 to estimate rates of substance use and service use. The fact that 62 OEF/OIF Veterans presenting for new PTSD examinations were examined during a six-month period at VA Connecticut, suggests a rate of 124 per year. According to CPRS, between 5/1/12-8/1/12 there were a total of 376 mental health exams scheduled of which 117 were for people not currently service-connected.

i. A rule-out or definitive diagnosis of alcohol abuse was made in eighteen Veterans and two additional Veterans had a substance abuse diagnosis for a total of 32% with an alcohol and/or substance abuse diagnosis. This likely underestimates the rates of substance use and risky drinking because chart review is an insensitive way to identify Veterans with substance use problems (Hawkins, Kivlahan et al. 2007). Only 3% of claimants had received any substance abuse treatment at VA during the three months before the evaluation and only 47% had received any mental health treatment. Altogether, 61% were diagnosed with PTSD on the Compensation examinations and 39% were not.

These results suggest that there is a high prevalence of substance use among OEF/OIF Veterans applying for PTSD-related Compensation, an unmet need for substance abuse treatment, and a range of PTSD-symptom severities.

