#### H. Chart Review and Database Extraction

1. Therapy Attendance and Service Use Outcomes. Episodes reflecting use of VA substance abuse, specialized PTSD and other mental health treatment will be collected from VA administrative records as described previously (Harpaz-Rotem, Rosenheck et al. 2009). The investigators have extensive experience analyzing VA service use data. [name] is a national authority on service use analyses.

The Austin Information Technology Center provides the service use data for [name] analyses. The Austin databases hold data from all Veterans who received any services from anywhere in VA. The Patient Treatment File contains all episodes of inpatient care delivered within the VA system. The Outpatient Encounter File documents all outpatient VA service use. VA bed section codes indicate hospitalization on specialized units and VA clinic codes indicate outpatient treatment in specialized clinics. In a recent manuscript, [name] describes analysis of psychotherapy service use codes from these databases (Hunt and Rosenheck, 2011), which will be extracted as psychotherapy participation may reflect a more specific measure of engagement in treatment than broader measures.

Service use data will be collected from three months before the Compensation claim was filed until three months after claims adjudication. We will also collect the date Veteran was separated from military service to determine when VA services became available to each Veteran.

2. Compensation examinations of each Veteran will be reviewed by research assistants who will complete a chart extraction form. The extraction form collates the following information:

- i. Clinician diagnosis from C&P exam
- ii. Alcohol Use

-- Level of detail describing alcohol use (No mention, Impression but no number of drinks, or number of drinks---including a statement that there has been no recent use).

- Amount of alcohol reported used in drinks/drinking day
- Alcohol Use Consequence (no mention, consequences listed)
- Alcohol Use Disorder Diagnosed (no diagnosis; use noted but no judgment that it is a problem, or merits intervention; rule-out alcohol use diagnosis made; alcohol use diagnosis made)

iii. Other Substance Use (characterized as for alcohol, with delineation of particular drugs)

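### The J.5 models of beliefs and attendance do not commit to adjusting for attendance before the examination, so an association could reflect prior engagement in care

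*Combined protocol and SAP*

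**What the plan says.** Section J.5 (Evaluative Specific Aim 2) fits HLM regressions of attendance, and other outcomes, on the Disability Beliefs Scale subscales, the Disability Application Appraisal Inventory subscales and their interactions. It asks whether the outcomes "are predicted by the following, after accounting for appropriate covariates". The covariates are then described: "Covariates in these analyses will include those reflecting three main domains that have been associated with treatment attendance". The named variables are age and gender; site and distance from home; and substance use, CAPS total and Beck Depression Inventory. Attendance before the examination is not among them.

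Section J.4, for Aim 1, has a rule that J.5 neither repeats nor refers to: "Baseline level of the dependent variable, e.g. CAPS-rated PTSD severity, will be included in the analysis as a covariate".

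The data exist. Section H.1 states: "Service use data will be collected from three months before the Compensation claim was filed until three months after claims adjudication". The Service Use Calendar is administered at baseline and covers the preceding 60 days, including non-VA care. Both belief instruments are scheduled at baseline only. In the chart review of 62 Veterans at VA Connecticut under Feasibility, "only 47% had received any mental health treatment" in the three months before the evaluation.

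**The concern.** Prior attendance is an obvious candidate predictor of later attendance, and it has already happened when beliefs are measured. A Veteran already in care may be more inclined to think that attending helps a claim, and may also be more likely to keep attending. Without prior attendance in the model, an association between belief and later attendance can arise from that route alone.

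The plan treats this variable as important elsewhere. Current enrollment in VA psychiatric or substance abuse treatment is an urn factor for the trial, and attendance before the examination is a regressor in the J.7 award analysis. The listed CAPS covariate is not an evident substitute: the Background reports an earlier study in which service use was unrelated to self-reported PTSD severity.

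What is at stake is the reading of Evaluative Hypothesis 2. The Significance section describes beliefs as probable determinants of outcome and as modifiable. An association that may be carried by prior engagement does not support that policy reading.

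**Working it through.** The plan gives no power, effect size or sample-size figure for Hypothesis 2, so there is no figure of its own to reproduce. The check has two parts.

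**1. Sections side by side**

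| Section | Outcome | Prior level or prior attendance in the model? |
|---|---|---|
| J.4 | CAPS, attendance | Yes: baseline level of the dependent variable |
| J.5 | Attendance (and others) | Not named |
| J.6 | Attendance before and after examination and award | Pre-examination attendance is part of the outcome; attitude interaction is secondary, for Aim 3 |
| J.7 | Award | Yes: attendance before the examination |

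**2. Possible size, with no true belief effect**

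Inputs from the documents: N = 560 (the sample in J.1, stated there for the substance-use analysis); share in care beforehand p = 0.47; 12 follow-up weeks.

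Assumptions, because the documents give no values: belief is d SD higher among those already in care; weekly attendance is 25%, 35% or 50% for them and 15% for the others, constant over the 12 weeks. The other J.5 covariates are left out.

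The difference in weeks attended is Δ = 12 × (difference in weekly rate): 12 × 0.10 = 1.2, 12 × 0.20 = 2.4 and 12 × 0.35 = 4.2 weeks.

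The expected unadjusted slope per SD of belief is p(1 − p)·d·Δ / √(1 + p(1 − p)d²), with p(1 − p) = 0.47 × 0.53 = 0.2491.

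- d = 0.2: 0.2491 × 0.2 / √1.00996 = 0.0496, times Δ gives 0.06, 0.12 and 0.21 weeks.
- d = 0.3: 0.2491 × 0.3 / √1.0224 = 0.0739, times Δ gives 0.09, 0.18 and 0.31 weeks.

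Simulated slopes agree: 0.117 and 0.178 weeks at 35% versus 15%; 0.210 and 0.313 at 50% versus 15%.

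Rejection rates at two-sided 0.05, from regressing weeks attended on belief:

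| Weekly attendance, prior care vs none | Unadjusted, d = 0.2 | Unadjusted, d = 0.3 |
|---|---|---|
| 25% vs 15% | 10% | 17% |
| 35% vs 15% | 12–20% | 21–38% |
| 50% vs 15% | 24–33% | 46–64% |

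Ranges in the last two rows cover 1,000 to 1,500 runs per setting under beta-binomial and logistic-normal between-person variation. The first row is a single specification; wider between-person spread would lower it. With a yes/no indicator of prior care added, the rate is about 5% throughout. At d = 0 the unadjusted rate is also about 5%.

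**Sensitivity**

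- *Sample size.* J.5 does not restate its sample. N = 640 gives the same pattern: 27% and 50% at 50% versus 15%.
- *Share in care.* The Background cites a study in which 112 of 452 (25%) used mental health services before claiming. With 25% in care, the rates at d = 0.2 and 0.3 are 14% and 27% (35% versus 15%) and 26% and 51% (50% versus 15%).
- *Slope rather than level.* A belief-by-time slope test rejects in 4–7% of runs without adjustment. This depends on attendance being flat over the weeks.
- *Belief came first.* If belief drives prior care (log-odds 0.3 to 0.5 per SD) and prior care drives later attendance, detection in these runs is 39–96% unadjusted and about 5% adjusted.

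**The case against.** A reader might infer that the omission will make beliefs look like a cause of attendance, or that false-positive rates as high as 79% (belief 0.4 SD higher, weekly attendance 50% versus 15%) describe this study. The documents do not support either. Bias needs a belief difference by prior care and persistence of attendance, and neither is quantified. The 47% counts any mental health treatment, from 62 charts at one site, so a single visit qualifies; nothing shows that such Veterans attend half of all weeks. This part of the objection stands.

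J.5 also does not say whether its test concerns level or slope, and J.4 focuses on slopes. That stands too: the problem is one of level. Hypothesis 2, however, concerns attendance being predicted by beliefs, which most naturally includes level.

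Adjustment can remove a real effect. The Background cites the claim that some Veterans enter treatment to further a disability claim, and baseline comes after filing. For them prior attendance is a mediator. This stands, and it rules out replacing the unadjusted model with the adjusted one.

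The reverse route is most plausible for the belief that attending helps a claim. It is less evident for the reasons-for-applying subscales. For the belief that substance abuse treatment harms a claim, the chart review found only 3% in such treatment at VA beforehand.

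Finally, the covariate wording is open-ended, and J.6 might expose the problem. But open wording commits to nothing, and the J.6 interaction is secondary and serves another aim.

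**Conclusion.** The omission is real and worth correcting. As written, J.5 could report an association between belief and level of attendance that reflects prior engagement. The false-positive rate could lie anywhere from the nominal 5% to well above half, depending on two quantities the documents do not give; the ranges in the working are illustrations, not estimates for this study. A reader might go further and conclude that Hypothesis 2 cannot be tested, or that the SBIRT comparison is affected. Neither follows: the data to separate the readings are largely collected, and J.5 is an observational analysis apart from the randomised comparison. Adjustment alone does not settle direction, because beliefs are measured once.

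**What to change.** State in J.5 that each attendance model will be reported twice: with the listed covariates, and with pre-examination attendance added. Define that covariate from VA records for the three months before the examination and from the 60-day baseline Service Use Calendar for non-VA care; a three-month window is not available for non-VA care. Report the belief associations by prior-care status as well, naming Veterans not in care at baseline as the cleanest test. State whether the test concerns level, slope or both. Conclude that beliefs predict attendance beyond prior engagement only if the adjusted result supports it.

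The cost is a few lines of text and some extra tables, with no new data collection. The drawback is that the adjusted estimate understates the effect if belief drove the earlier attendance, and the subgroup not in care is smaller: about 0.53 × 560 = 297 Veterans if the 47% holds.
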